**9.1. Appendix 1: Time & Events**

**9.1.1. Protocol Defined Time & Events**

**Time and Events Tables (Groups A, B, C, D, and E)**

Procedure	Screening (up to 30 days prior to Day -1)	Check-in	Treatment Period (Days)			Follow-up (10 [±5] days post-last dose) or Early Termination	Notes
		-1	1	2	3		
Confined to clinic		X	X	X	X		Subjects will be admitted to the clinic on Day -1 and will be discharged on Day 3. Confinement will be 4 days and 3 overnight stays
Informed consent	X						
Inclusion and exclusion criteria	X	X					
Demographics	X						
Complete physical examination including height and weight	X						
Abbreviated physical examination		X			X	X	
Medical history (includes substance usage and history of renal disease)	X						Substances: drugs, alcohol, and caffeine. Subjects with renal impairment should be on a stable regimen of chronic medications 7 days before the first dose of study drug on Day 1.
Past and current medical conditions (including renal impairment medical history and eGFR)	X						eGFR as defined in the FDA draft guidance for industry, "Pharmacokinetics in Patients with Impaired Renal Function" [DHHS, 2010]  Subjects with normal renal function will also be classified based on Clcr.

Procedure	Screening (up to 30 days prior to Day -1)	Check-in	Treatment Period (Days)			Follow-up (10 [±5] days post-last dose) or Early Termination	Notes
			-1	1	2		
Serum or urine pregnancy test/FSH	X	X				X	Serum (or urine) pregnancy test (if WCBP); estradiol and FSH at Screening, as appropriate
HIV antibody, hepatitis B surface antigen, and hepatitis C antibody testing a	X						
Drug and alcohol screen	X	X					See protocol Table 6.
Laboratory assessments (include liver chemistries)	X	X		X		X	Including serum chemistry, hematology and urinalysis. Results from 24 hours after dosing should be available before discharge on Day 3.
12-lead ECG	X	X	X	X	X	X	
Vital signs	X	X	X	X	X	X	Respiratory rate and body temperature collected at Screening only.
Genetic sample b		X					Collect a pharmacogenomics (PGx) sample only if the subject has a signed consent specific for this purpose. The PGx sample can be collected anytime, but Day -1 is recommended.
Study drug administration			X				
Blood collection for pharmacokinetics			X	X	X		See protocol Table 3 for time points.
Urine collection for pharmacokinetics			X	X	X		Subjects with normal renal function and subjects with renal impairment will have different collection intervals. See protocol Table 3 for time points.
Saliva collection for pharmacokinetics c			X	X	X		See protocol Table 3 for time points.
AE/SAE review	X	X	←-----→			X	
Concomitant medication review		X	←-----→			X	

AE = adverse event, Clcr = estimated creatinine clearance; eGFR = estimated glomerular filtration rate, ECG = electrocardiogram, FSH = follicle stimulating hormone; HIV = human immunodeficiency virus; PGx = pharmacogenetic, SAE = serious AE; WCBP = women of childbearing potential.

- a If test has otherwise been performed within 3 months before the first dose of study treatment, testing at Screening is not required.
- b Informed consent for optional substudies (e.g., genetics research) must be obtained before collecting a sample.
- c Subjects in Part 1 only. It should be noted that subjects with renal impairment may be on medications that may prevent saliva collections.

**Safety and PK Assessments (Groups A, B, C, D, and E)**

Procedure a	Predose	Treatment Period Time point (hours)														
		0	0.25	0.5	1	1.5	2	2.5	3	4	6	8	12	24 b	36 b	48 b
12-lead electrocardiogram	X					X	X			X		X	X	X	X	X
Vital signs	X					X	X			X		X	X	X	X	X
Treatment administration 2-hour IV gepotidacin infusion		X														
Blood collection for pharmacokinetics	X		X	X	X	X	X	X	X	X	X	X	X	X	X	X
Urine collection for pharmacokinetics (subjects with normal renal function) c	X	X					X			X	X	X	X	X	X	
Urine collection for pharmacokinetics (subjects with renal impairment) d	X	X								X		X	X	X	X	
Saliva collections e	X		X	X	X	X	X	X	X	X	X	X	X	X	X	X

- a When coinciding with safety and/or pharmacokinetic assessments, electrocardiograms, vital signs, and pharmacokinetic blood collections should be performed in said order.
- b The 24-, 36-, and 48-hour postdose time points correspond to time points on Day 2 and 3, respectively.
- c Urine collection intervals for subjects with normal renal function (Group A and Group D) include 0 (pre-dose), 0 to 2 hours, 2 to 4 hours, 4 to 6 hours, 6 to 8 hours, 8 to 12 hours, 12 to 24 hours, 24 to 36 hours, and 36 to 48 hours.
- d Urine collection intervals for subjects with renal impairment (Group B, Group C, and Group E) include 0 hour (pre-dose), 0 to 6 hours, 6 to 12 hours, 12 to 24 hours, 24 to 36, and 36 to 48 hours.
- e Subjects in Part 1 only. It should be noted that subjects with renal impairment may be on medications that may prevent saliva collections.

**Time and Events Tables (Group F)**

Procedure a	Screening (up to 30 days prior to Day -1)	Check -in	Treatment Period (Days)								Follow-up (10 [±5] days post-last dose) or Early Termination	Notes
			1				2					
			-1	1	2	3	4 to 6	7	8	9		
Confined to clinic b		X	X	X	X		X	X	X	X		Subjects will be admitted to the clinic on Day -1 and Day 7, and will be discharged on Day 3 (Period 1) and Day 10 (Period 2). Confinement will be 8 days and 6 overnight stays) total.
Informed consent	X											
Inclusion and exclusion criteria	X	X					X					
Demographics	X											
Complete physical examination including height and weight	X											
Abbreviated physical examination		X					X			X	X	
Medical history (includes substance usage and history of renal disease)	X											Substances: drugs, alcohol, and caffeine. Subjects with renal impairment should be on a stable regimen of chronic medications 7 days before the first dose of study drug on Day 1.

Procedure a	Screening (up to 30 days prior to Day -1)	Check -in	Treatment Period (Days)								Follow-up (10 [±5] days post-last dose) or Early Termination	Notes	
			1				2						
			-1	1	2	3	4 to 6	7	8	9			10
Past and current medical conditions (including renal impairment medical history and eGFR)	X												eGFR defined in the FDA draft guidance for industry, [DHHS, 2010]
Serum or urine pregnancy test/FSH	X	X					X					X	Serum (or urine) pregnancy test (if WCBP); estradiol and FSH at Screening as appropriate.
HIV antibody, hepatitis B surface antigen, and hepatitis C antibody testing c	X												
Drug and alcohol screen	X	X					X						See protocol Table 6.
Laboratory assessments (include liver chemistries)	X	X		X			X		X			X	Including serum chemistry, and hematology. Results from 24 hours after dosing should be available before discharge on Day 3 (Period 1) and Day 10 (Period 2)
12-lead ECG	X	X	X	X	X		X	X	X	X		X	
Vital signs	X	X	X	X	X		X	X	X	X		X	Respiratory rate and body temperature collected at Screening only.

Procedure a	Screening (up to 30 days prior to Day -1)	Check -in	Treatment Period (Days)								Follow-up (10 [±5] days post-last dose) or Early Termination	Notes	
			1				2						
			-1	1	2	3	4 to 6	7	8	9			10
Genetic sample d		X											Collect a pharmacogenomics (PGx) sample only if the subject has a signed consent specific for this purpose. The PGx sample can be collected anytime, but Day -1 is recommended.
Study drug administration			X b					X b					
Blood collection for pharmacokinetics			X	X	X			X	X	X			See protocol Table 5 for time points.
Urine collection for pharmacokinetics			X	X	X			X	X	X			See protocol Table 5 for time points. Subjects may not be able to produce a urine sample.
Dialysate collections for pharmacokinetics			X	X	X								See protocol Table 5 for time points.
AE/SAE review	X	X	←=====→								X		
Concomitant medication review		X	←=====→					←=====→			X		

AE = adverse event, eGFR = estimated glomerular filtration rate, ECG = electrocardiogram, FSH = follicle-stimulating hormone; HIV = human immunodeficiency virus, PGx = pharmacogenetic, SAE = serious AE; WCBP = women of childbearing potential.

- a For subjects on hemodialysis (Part 2 [optional], Group F), assessments performed on scheduled hemodialysis days are to be done before hemodialysis (except for PK sample collection, which will be done before and after hemodialysis).
- b Subjects in Group F will participate in 2 treatment periods, with dosing in these periods separated by a washout period of at least 7 days. Subjects in Group F will enter the clinic at Check-in (Day -1, Period 1 and Day 7, Period 2) before each study drug administration (Day 1, Period 1 and Day 8, Period 2). On Day 1 (Period 1) and Day 8 (Period 2), subjects in Group F will receive a single dose of study drug as follows: gepotidacin 750 mg administered as a 2-hour IV infusion starting approximately 2 hours before initiation of the last hemodialysis session of the week (Period 1) and gepotidacin 750 mg administered as a 2-hour IV infusion starting within 2 hours after completion of the last hemodialysis session of the week (Period 2). Subjects in Group F will be discharged from the clinic on Day 10, Period 2.
- c If test has otherwise been performed within 3 months prior to first dose of study treatment, testing at Screening is not required.
- d Informed consent for optional substudies (e.g., genetics research) must be obtained before collecting a sample.

## Safety and PK Assessments (Group F)

Procedure a	Predose	Treatment Periods 1 and 2 Time point (hours) a														
		0	0.25	0.5	1	1.5	2	2.5	3	4	6	8	12	24 b	36 b	48 b
12-lead electrocardiogram	X						X c			X		X	X	X	X	X
Vital signs	X						X c			X		X	X	X	X	X
Treatment administration 2-hour IV gepotidacin infusion d		X														
Blood collection for pharmacokinetics	X		X	X	X	X	X	X	X	X	X	X	X	X	X	X
Urine collection for pharmacokinetics e	X	X										X	X	X	X	X
Dialysate collection for pharmacokinetics f	X	X		X		X		X								

a When coinciding with safety and/or pharmacokinetic assessments, electrocardiograms, vital signs, and pharmacokinetic blood collections should be performed in said order.

b The 24-, 36-, and 48-hour postdose time points correspond to time points on Day 2 and 3, respectively.

c Performed post infusion.

d Subjects in Group F will participate in 2 treatment periods, with dosing in these periods separated by a washout period of at least 7 days. Subjects in Group F will enter the clinic at Check-in (Day -1, Period 1 and Day 7, Period 2) before each study drug administration (Day 1, Period 1 and Day 8, Period 2). On Day 1 (Period 1) and Day 8 (Period 2), subjects in Group F will receive a single dose of study drug as follows: gepotidacin 750 mg administered as a 2-hour IV infusion starting approximately 2 hours before initiation of the last hemodialysis session of the week (Period 1) and gepotidacin 750 mg administered as a 2-hour IV infusion starting within 2 hours after completion of the last hemodialysis session of the week (Period 2). Subjects in Group F will be discharged from the clinic on Day 10, Period 2.

e It should be noted that subjects in Group F may not be able to produce urine samples due to their medical condition. All sampling times are relative to the start of the infusion.

f Dialysate fluid will be collected on Day 1 after dosing (Period 1 only) over each 1-hour collection interval of the hemodialysis session.

## 9.2. Appendix 2: Treatment States and Phases

### 9.2.1. Treatment Phases

Assessments and events will be classified according to the time of occurrence relative to dosing.

Treatment Phase	Definition
Pre-Treatment	Date/Time < Study Treatment Start Date/Time
On-Treatment	Study Treatment Start Date/Time ≤ Date/Time ≤ Study Treatment Stop Date/Time
Post-Treatment	Date/Time > Study Treatment Stop Date /Time

### 9.2.2. Treatment States

For Groups A, B,C, D, and E, assessments and events will be classified according to time of occurrence relative to the start and/or stop date of the study treatment.

For Group F, assessments and events will be classified according to the time of occurrence relative to dosing for the respective session.

#### 9.2.2.1. Treatment States for Safety Data

Treatment State	Definition
Pre-Treatment	Date/Time < Study Treatment Start Date/Time
On-Treatment	Study Treatment Start Date/Time ≤ Date/Time ≤ Study Treatment Stop Date/Time + 2 Days
Post-Treatment	Date/Time > Study Treatment Stop Date/Time +2 Days

#### NOTES:

- If the study treatment stop date is missing then the assessment will be considered to be On-Treatment

#### 9.2.2.2. Treatment States for AE Data

Treatment State	Definition
Pre-Treatment	AE Start Date/Time < Study Treatment Start Date/Time
On-Treatment	If AE onset date/time is on or after treatment start date/time & on or before treatment stop date/time with 2 days lag time. Study Treatment Start Date/Time ≤ AE Start Date/Time ≤ Study Treatment Stop Date/Time + 2 Days
Post-Treatment	If AE onset date/time is after the treatment stop date/time with 2 days lag time. AE Start Date/Time > Study Treatment Stop Date/Time + 2 Days
Onset Time Since 1 st Dose (Days)	If Treatment Start Date/Time > AE Onset Date/Time, = AE Onset Date - Treatment Start Date If Treatment Start Date/Time ≤ AE Onset Date/Time, = AE Onset Date - Treatment Start Date +1 Missing otherwise.
Duration (Days)	AE Resolution Date – AE Onset Date + 1

Treatment State	Definition
Drug-related	If relationship is marked 'YES' on CRF OR value is missing.

**NOTES:**

- If the study treatment stop date is missing then the AE will be considered to be On-Treatment.

### 9.3. Appendix 3: Data Display Standards & Handling Conventions

#### 9.3.1. Study Treatment & Sub-group Display Descriptors

Treatment Group Descriptions				
Study Part [1]	Renal Impairment Group		Data Displays for Reporting	
	Code	Description	Description	Order [2]
1	A	Normal Renal Function	Normal	1
1	B	Moderate Renal Impairment	Moderate	2
1	C	Severe Renal Impairment and ESRD not on Hemodialysis	Severe/ESRD not on hemodialysis	3
2	D*	Normal Renal Function	Normal	4
2	E	Mild Renal Impairment	Mild	5
2	F	Severe Renal Impairment with ESRD and on Hemodialysis	ESRD on hemodialysis	6

#### NOTES:

1. TFLs will be presented separately for Part 1 and Part 2 of the study.
2. Order represents treatments being presented in TFL, as appropriate.
3. \* If there are a sufficient number of subjects with normal renal function enrolled in Part 1 (Group A) that match subjects with renal impairment in other groups, a determination will be made regarding the enrollment of matching subjects with normal renal function in Part 2 (Group D).

#### 9.3.2. Baseline Definition & Derivations

##### 9.3.2.1. Baseline Definitions

For all endpoints (except as noted in baseline definitions) the baseline value will be the latest pre-dose assessment and are applicable to each period. For Groups A, B, C, D, and E there is one treatment period and the baseline value will be the latest pre-dose assessment in that period.

Parameter	Study Assessments Considered As Baseline			Baseline Used in Data Display
	Screening	Day -1	Day 1 (Pre-Dose)	
Safety				
Hematology	X	X		Day -1
Clinical Chemistry	X	X		Day -1
12 Lead ECG	X	X	X	Day 1 (Pre-dose)
Vital Signs	X	X	X	Day 1 (Pre-dose)

#### NOTES :

- Unless otherwise stated, the mean of replicate assessments at any given time point will be used as the value for that time point.

**9.3.2.2. Derivations and Handling of Missing Baseline Data**

Definition	Reporting Details
Change from Baseline	= Post-Dose Visit Value – Baseline

**NOTES :**

- Unless otherwise specified, the baseline definitions specified in Section 9.3.2.1 Baseline Definitions will be used for derivations for endpoints / parameters and indicated on summaries and listings.
- Unless otherwise stated, if baseline data is missing no derivation will be performed and will be set to missing.
- The baseline definition will be footnoted on all change from baseline displays.

**9.3.3. Reporting Process & Standards**

Reporting Process
Software

 
• The currently supported versions of SAS software [Insert Other Software as Required] will be used.
 

Analysis Datasets

 
• Analysis datasets will be created according to CDISC standards (SDTM IG Version 3.1.3 & AdaM IG Version 1.0).
 
• For creation of ADaM datasets (ADCM/ADAE), the same version of dictionary datasets will be implemented for conversion from SI to SDTM.
 

Generation of RTF Files

 
• RTF files will be generated for all reporting efforts described in the RAP.
 

Reporting Standards
General

 
• The current GSK Integrated Data Standards Library (IDSL) will be applied for reporting, unless otherwise stated:                             
 
○ 4.03 to 4.23: General Principles
 
○ 5.01 to 5.08: Principles Related to Data Listings
 
○ 6.01 to 6.11: Principles Related to Summary Tables
 
○ 7.01 to 7.13: Principles Related to Graphics
 
 
 

Formats

 
• All data will be reported according to the actual treatment the subject received unless otherwise stated.
 
• GSK IDSL Statistical Principles (5.03 & 6.06.3) for decimal places (DP's) will be adopted for reporting of data based on the raw data collected.
 
• Numeric data will be reported at the precision collected on the eCRF.
 
• The reported precision from non eCRF sources will follow the IDSL statistical principles but may be adjusted to a clinically interpretable number of DP's.
 

Planned and Actual Time

 
• Reporting for tables, figures and formal statistical analyses :                             
 
• Planned time relative to dosing will be used in figures, summaries, statistical analyses and calculation of any derived parameters, unless otherwise stated.
 
• The impact of any major deviation from the planned assessment times and/or scheduled
 
 
 

Reporting Standards	

visit days on the analyses and interpretation of the results will be assessed as appropriate.
 
 
Reporting for Data Listings:                             
 
Planned and actual time relative to study drug dosing will be shown in listings (Refer to IDSL Statistical Principle 5.05.1).
 
Unscheduled or unplanned readings will be presented within the subject's listings.
 
Visits outside the protocol defined time-windows (i.e. recorded as protocol deviations) will be included in listings but omitted from figures, summaries and statistical analyses.
 
 
 
	
Unscheduled Visits	

 
Unscheduled visits will not be included in summary tables.
 
Unscheduled visits will not be included in figures.
 
All unscheduled visits will be included in listings.
 
	
Descriptive Summary Statistics	
Continuous Data	Refer to IDSL Statistical Principle 6.06.1
Categorical Data	N, n, frequency, %
Reporting of Pharmacokinetic Concentration Data	
Descriptive Summary Statistics	Refer to IDSL Statistical Principle 6.06.1 Assign zero to NQ values (Refer to GUI_51487 for further details)
Reporting of Pharmacokinetic Parameters	
Descriptive Summary Statistics (Log Transformed)	
N, n, geometric mean, 95% CI of geometric mean, standard deviation (SD) of logged data and [between and or within] geometric coefficient of variation (CVb/w (%)) will be reported.
 $CV_b (\%) = \sqrt{(\exp(SD^2) - 1) * 100}$ 
(SD = SD of log transformed data)

Parameters Not Being Log Transformed	T max , %AUC ex , lambda z , lambda z_lower , lambda z_upper , lambda z_no. of points , t last
Summary Tables	lambda z_lower , lambda z_upper , lambda z_no. of points , t last
Listings	
Include all following PK parameters:
 
Plasma - Cmax, AUC0-∞, AUC0-t, t1/2, Tmax, %AUCex, tlast, lambdaz, lambdaz_lower, lambdaz_upper, lambdaz_no. of points, Vss, Vz, CL
 
Urine - Ae total, Ae(t1-t2), AUC(0-12), AUC(0-24), AUC(0-48), fe%, CLr
 
Dialysate - Arem(0-1), Arem(1-2), Arem(2-3), Arem(3-4), Arem(0-4), AUC(t0-t1), CLD, Frem%(0-4)
 
Saliva - Cmax, AUC0-∞, AUC0-t, t1/2, CL, Vss, Vz, Tmax, %AUCex, tlast, lambdaz, lambdaz_lower, lambdaz_upper, lambdaz_no. of points, RAUC(0-t), RAUC(0-∞)

Graphical Displays	

 
Refer to IDSL Statistical Principals 7.01 to 7.13.
 
	

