7.3.5. Electrocardiogram

- Single 12-lead ECGs will be obtained at each time point during the study using an ECG machine that automatically calculates the heart rate and measures PR, QRS, QT, and QTc intervals. Refer to Section [5.4.2](#) for QTc withdrawal criteria and additional QTc readings that may be necessary.

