All laboratory tests with values that are considered clinically significantly abnormal during participation should be repeated until the values return to normal or baseline. If such values do not return to normal within a period judged reasonable by the investigator, the etiology should be identified and the sponsor notified.

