## 9.5. Appendix 5: Premature Withdrawals & Handling of Missing Data

### 9.5.1. Premature Withdrawals

Element	Reporting Detail
General	
 
• Subject study completion (i.e. as specified in the protocol) was defined as one who has completed all phases of the study including the follow-up visit.
 
• Withdrawn subjects may be replaced in the study.
 
• All available data from subjects who were withdrawn from the study will be listed and all available planned data will be included in summary tables and figures, unless otherwise specified.
 

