## 9.11.5. Safety Tables

Safety : Tables					
No.	Population	IDSL / TST ID / Example Shell	Title	Programming Notes	Deliverable [Priority]
Adverse Events					
2.1	Safety	AE2	Relationship of Adverse Event System Organ Classes, Preferred Terms and Verbatim Text		SAC [1]
2.2	Safety	AE1	Summary of All Adverse Events		SAC [1]
Laboratory Measurements					
2.3	Safety	LB1	Summary of Clinical Chemistry Change from Baseline		SAC [1]
2.4	Safety	LB1	Summary of Haematology Change from Baseline		SAC [1]
2.5	Safety	UR3b	Summary of Urinalysis Dipstick Results		SAC [1]
Electrocardiograms					
2.6	Safety	EG1	Summary of ECG Findings		SAC [1]
2.7	Safety	SAFE_T1	Summary of Frequency of Maximum Post-Dose ECG Parameter Corrected QTc Interval		SAC [1]
2.8	Safety	SAFE_T2	Summary of Frequency of Maximum Change from Baseline for ECG Parameter Corrected QTc Interval		SAC [1]
2.9	Safety	EG2	Summary of Change from Baseline in ECG Values		SAC [1]
Vital Signs					
2.10	Safety	VS1	Summary of Change from Baseline in Vital Signs		SAC [1]

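### The SAP's rule against unscheduled visits in summary tables has no exception for the maximum-QTc tables (2.7 and 2.8), so their counts can be too low

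*SAP*

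**What the plan says.** SAP 9.3.3 sets general reporting rules:

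- On unscheduled visits: "Unscheduled visits will not be included in summary tables". A parallel line bars them from figures, and a third sends them to listings.
- On single readings: "Unscheduled or unplanned readings will be presented within the subject's listings". No line puts such readings into a table.
- On visits outside the protocol windows: these "will be included in listings but omitted from figures, summaries and statistical analyses".
- On the time basis: "Planned time relative to dosing will be used in figures, summaries, statistical analyses and calculation of any derived parameters, unless otherwise stated".

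SAP 9.5.1 says of withdrawn subjects that "all available planned data will be included in summary tables and figures, unless otherwise specified".

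The list of safety tables in SAP 9.11.5 includes Table 2.7, "Summary of Frequency of Maximum Post-Dose ECG Parameter Corrected QTc Interval", and Table 2.8, the matching table for maximum change from baseline. The programming notes for both are empty.

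On the protocol side, Section 7.3.5 specifies a single ECG at each time point and points to Section 5.4.2 for withdrawal criteria and "additional QTc readings that may be necessary". Section 9.4.2.1 commits to summarizing ECG abnormalities of any kind by group, with QTc above 500 msec as a named example, and does not limit this to scheduled readings. SAP 2.1 declares no departure from the protocol's planned analysis.

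**The concern.** Keeping only planned readings is sensible for a mean at a given hour. It does not suit a table whose purpose is each subject's worst value. Extra ECGs tend to be taken because a scheduled reading or a symptom raised a question, so the readings left out are not a random subset. If one of them is the subject's highest, the table reports a lower maximum than the one observed.

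QT prolongation is a named risk in Protocol 4.6.1, and ECG readings belong to a secondary objective. Tables 2.7 and 2.8 are where a reader would look for the number of subjects who crossed a QTc threshold. A listing holds the missing reading but does not correct the count.

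**Working it through.** The plan gives no figure to reproduce. The check is textual, with a short calculation for scale.

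**1. Does the rule reach Tables 2.7 and 2.8?** Both are summary tables. The rule covers summary tables without exception, and neither table carries a programming note that lifts it. The SAP does use that column for such instructions elsewhere: the notes to Listings 41 to 45 ask for unscheduled concentration data to be shown.

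**2. Does another clause let the readings in?** SAP 9.4.1 averages several measurements at one time point. Of two values in a window it keeps the one nearer the target, or the mean if they are equally distant. Neither preserves a maximum. If a scheduled value is s and a repeat is r > s, the mean is (s + r)/2 < r. The nearest-to-target rule keeps r only if r happens to lie closer to the planned time.

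**3. What is lost, and in which direction?** Let S be a subject's highest scheduled post-dose QTc and U the highest unscheduled one. The table uses S, while the observed maximum is M = max(S, U), and M ≥ S always. So the number of subjects at or above any threshold can fall or stay the same, but never rise. For Table 2.8 this holds with the baseline value fixed. A subject is misplaced only if U > S and a category boundary lies between them. SAP 9.6.1 gives boundaries at 450, 480 and 500 msec, and at 30 and 60 msec for the increase; I assume the two tables use these. A scheduled abnormal reading that prompts a repeat is part of S and still counts.

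**4. Where could U exceed S?** In Groups A to E the first scheduled post-dose ECGs are at 1.5, 2, 4, 8 and 12 hours (Protocol Table 3). In Group F they are at 2, 4, 8 and 12 hours (Protocol Table 5). Protocol 4.6.1 describes a QT effect that builds up during the 2-hour infusion and wears off over the 2 hours after it ends. The possible cases are a repeat that is worse than the scheduled reading, or a symptom-prompted ECG between scheduled times, for example between 2 and 4 hours.

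**5. Protocol against SAP.** Protocol 9.4.2.1 summarizes any ECG abnormality by group. A maximum taken only over scheduled readings is narrower than that, yet SAP 2.1 records no change.

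**6. Size.** One misplaced subject moves a category by 100/n percentage points. Group sizes are from Protocol 4.3:

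| n | Group | 100/n |
|---|---|---|
| 16 | Normal function, Part 1 (upper limit) | 6.25 |
| 8 | Impaired groups, Part 1 | 12.5 |
| 4 | Part 2 groups (lower limit) | 25 |

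The documents do not say how often a subject's category would rest on an unscheduled ECG. With an assumed per-subject chance p, independent between subjects, the chance of at least one such subject in a group is 1 − (1 − p)^n:

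| p (assumed) | n = 8 | n = 4 |
|---|---|---|
| 2% | 1 − 0.98^8 = 15% | 1 − 0.98^4 = 8% |
| 5% | 1 − 0.95^8 = 34% | 1 − 0.95^4 = 19% |
| 10% | 1 − 0.90^8 = 57% | 1 − 0.90^4 = 34% |

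**The case against.** The strongest reply is that exclusion from these two tables is inferred, not stated. The rule speaks of visits, and for readings the SAP says only that they are listed. Subjects are confined from Day -1 to Day 3, so an extra ECG in that time could be called a further reading within a planned visit. Time points added by a note to file under Protocol Section 7 could count as planned. The shells for the two tables and the sponsor's display standards are not in the documents and may settle the matter. This stands as far as it goes, but no text available places an unscheduled reading in either table. That two programmers could read the rule differently is itself a reason to settle it.

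A second reply is that the loss is limited. The scheduled ECGs at the end of infusion and at 4 hours cover the expected peak and its decline. Protocol 7.3.5 only foresees extra readings, and Section 5.4.2 orders none. Abnormal ECGs judged clinically significant are adverse events (Protocol 12.5.1) and reach Table 2.2. All of this is fair and makes the problem smaller. It does not change the direction of the error or correct a count in Table 2.7.

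A reader might also infer more than the documents support:

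- **That laboratory summaries are affected in the same way.** The protocol does say: "All laboratory tests with values that are considered clinically significantly abnormal during participation should be repeated until the values return to normal or baseline". Those repeats mostly record recovery, however. Toxicity grades and values of potential clinical importance appear in SAP Appendix 11 only as listings (23 to 28 and 31 to 34), and listings keep unscheduled data.
- **That the out-of-window rule does similar harm.** Late visits are not prompted by abnormal findings. The post-dose visit window at issue is follow-up at 10 ± 5 days, long after the QT effect described in Protocol 4.6.1.
- **That the bias is largest in the impaired groups.** They may enter with a higher baseline QTcF (up to 480 against 450 msec), and predicted Cmax is higher in severe impairment (7.93 against 5.65 µg/mL). Neither fact shows that their maxima fall more often on unscheduled ECGs.

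**Conclusion.** The point holds for Tables 2.7 and 2.8. Applied as written, SAP 9.3.3 leaves unscheduled ECGs out of tables meant to show each subject's worst QTc. The counts at or above any threshold can only be too low, and the tables deliver less than Protocol 9.4.2.1 promises.

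The figures of 12.5 and 25 percentage points are what one subject is worth, not an estimate of bias. The probabilities in the working rest on assumed rates.

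The conclusion rests on two readings: that the general rule governs tables without a stated exception, and that an extra ECG taken in the clinic falls under it. The data themselves are not lost, since Listings 29 to 32 would show abnormal findings and ECG values of potential clinical importance.

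**What to change.** Add one sentence to SAP 9.3.3, and repeat it in the programming notes of Tables 2.7 and 2.8: these maximum tables use all post-dose ECG readings, scheduled or unscheduled. Say also that this overrides the averaging and nearest-to-target conventions of SAP 9.4.1 for these tables, and how an averaged triplicate (allowed by Protocol 5.4.2) enters. Keep the planned-reading rule for by-time-point summaries and figures.

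The cost is a programming flag, with no new data and no change to trial conduct. There is a small downside: a maximum over more readings tends to be higher, so subjects with more repeat ECGs have more chances of a high value. A footnote giving, by group, the number of subjects whose maximum came from an unscheduled reading would make that visible.
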